20.8 MISSING DATE INFORMATION FOR CONCOMITANT MEDICATIONS

For concomitant medications, incomplete (i.e., partial missing) start date and/or stop date will be imputed. When the start date and the stop date are both incomplete for a subject, consider to impute the start date first.

Missing day and month

- If the year of the incomplete start date is the same as the year of the date of the first dose of investigational product, then the day and month of the date of the first dose will be assigned to the missing fields.
- If the year of the incomplete start date is before the year of the date of the first dose of investigational product, then December 31 will be assigned to the missing fields.
- If the year of the incomplete start date is after the year of the date of the first dose of investigational product, then January 1 will be assigned to the missing fields.

Missing month only

- The day will be treated as missing and both month and day will be replaced according to the above procedure.

Missing day only

- If the month and year of the incomplete start date are the same as the month and year of the date of the first dose of investigational product, then the day of the first dose will be assigned to the missing day.
- If either the year is before the year of the date of the first dose of investigational product or if both years are the same but the month is before the month of the date of the first dose of investigational product, then the last day of the month will be assigned to the missing day.
- If either the year is after the year of the date of the first dose of investigational product or if both years are the same but the month is after the month of the date of the first dose of investigational product, then the first day of the month will be assigned to the missing day.

Incomplete Stop Date

Missing day and month

- If the year of the incomplete stop date is the same as the year of the date of the last dose of investigational product, then the day and month of the date of the last dose will be assigned to the missing fields.
- If the year of the incomplete stop date is before the year of the date of the last dose of investigational product, then December 31 will be assigned to the missing fields.
- If the year of the incomplete stop date is after the year of the date of the last dose of investigational product, then January 1 will be assigned to the missing fields.

Missing month only

- The day will be treated as missing and both month and day will be replaced according to the above procedure.

Missing day only

- If the month and year of the incomplete stop date are the same as the month and year of the date of the last dose of investigational product, then the day of the last dose will be assigned to the missing day.
- If either the year is before the year of the date of the last dose of investigational product or if both years are the same but the month is before the month of the date of the last dose of investigational product, then the last day of the month will be assigned to the missing day.

- If either the year is after the year of the date of the last dose of investigational product or if both years are the same but the month is after the month of the date of the last dose of investigational product, then the first day of the month will be assigned to the missing day.

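### Partial concomitant-medication stop dates in or after the last-dose month or year are set too early, with no check against the start date, so post-dosing use can be understated

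*SAP*

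**What the plan says.** SAP 20.8 has three branches for an incomplete stop date, each relative to the last dose.

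- **Later month or year.** With only the day missing, the stop is compared with the "date of the last dose of investigational product, then the first day of the month will be assigned to the missing day". With day and month missing, it is compared with the "year of the date of the last dose of investigational product, then January 1 will be assigned to the missing fields". Both give the earliest date the record allows.
- **Same month or year.** With the day missing, "then the day of the last dose will be assigned to the missing day". With day and month missing, "then the day and month of the date of the last dose will be assigned to the missing fields".
- **Earlier month or year.** With the day missing, the comparison is with the "date of the last dose of investigational product, then the last day of the month will be assigned to the missing day"; a year-only stop goes to 31 December. Both give the latest date the record allows.

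The only instruction linking the two dates is: "When the start date and the stop date are both incomplete for a subject, consider to impute the start date first". No sentence makes the stop fall on or after the start.

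SAP 9.3 applies Table 1 after this step. *During* runs from Day 1 to last dose + 28 days, and *Post* from last dose + 29. A medicine started by last dose + 28 is *During* only if its stop is inside that window, and *During, Post* if its stop is later or wholly missing. A start after last dose + 28 with a stop inside the window is *Data error*.

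**The concern.** Two things go wrong in the same-period and later-period branches. First, the completed stop can precede a start that is known or has itself been completed. The plan's own rule then makes an impossible record out of a valid one. If the start is after last dose + 28, the record can land in *Data error*, and the SAP does not say how such records are counted.

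Second, a stop that truly came after last dose + 28 can be moved back inside the window, so the medicine loses its *Post* label. This sits badly with Table 1. For a medicine started by last dose + 28, having no stop date at all gives *During, Post*, while a stop known to fall in a later month can give *During* only. Knowing more then yields less post-dosing use.

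The outputs at stake are Tables 14.1.5.3 and 14.1.5.7, Listing 16.2.11.2, and the post-dosing CNS depressant table promised in SAP 9.3 (which is absent from the table list in SAP Appendix 3). The timing is relevant: the schedule in Protocol Appendix 1 puts injection 6 at Day 141 and the follow-up call at Day 197, so a completer's last medication information is collected at about last dose + 56.

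**Working it through.** The plan gives no figure to reproduce here. The check applies SAP 20.8 and Table 1 literally.

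**Worked dates.** Take a last dose on 10 May 2017. The *During* window ends on 10 May + 28 = 7 June 2017.

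| Start | Recorded stop | Completed stop | Result |
|---|---|---|---|
| 1 April | June 2017 | 1 June | *During* only; a true stop on 8–30 June should be *During, Post* |
| 15 June | June 2017 | 1 June | stop before start; *Data error* |
| 15 June | 2017 | 10 May | stop before start; *Data error* |
| 20 May | May 2017 | 10 May | stop before start; still *During* |
| June 2017 (completed to 1 June) | 2017 | 10 May | stop before start, although the start was completed first |
| June 2017 (completed to 1 June) | June 2017 | 1 June | no inversion |
| 1 April | April 2017 | 30 April | latest date; no problem |

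**How often the first of the next month lies inside the window.** For a last dose on day d of a month with m days, the first of the next month is m − d + 1 days later. This is at most 28 when d ≥ m − 27, which holds for exactly 28 days in every month. So 12 × 28 = 336 of 365 last-dose dates (92%). The first of the month after that is never inside the window (0 of 365), so a day-missing stop two or more calendar months after the last-dose month is classified correctly.

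**Lost *Post* labels.** Assumptions: every last-dose date in 2017 equally weighted, a medicine started before the last dose, and true stops spread evenly over last dose + 29 to + 56. That gives 28 × 365 = 10,220 combinations.
- Day missing: 5,348 become *During* only (52%). Of these, 5,323 come from the next-month rule and 25 from the same-month rule.
- Day and month missing: 9,814 become *During* only (96%).
- In the other direction, none of the 29 × 365 = 10,585 combinations with a true stop from the last dose to last dose + 28 gains a false *Post* label.

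**Stops before starts.** Same grid, with courses of up to 14 days, a known start after the last dose, and a true stop by last dose + 56: 252,945 combinations.
- Day missing: 193,305 inverted (76%), of which 47,117 are *Data error* (19% of all).
- Day and month missing: 247,975 inverted (98%), of which 104,636 are *Data error* (41% of all).

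These shares describe the rule on an even grid, given that the stop date is partial. They are not estimates for the trial.

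**The case against.** A reader might infer that 20.8 always uses the earliest possible stop date. It does not. Stops before the last-dose month or year get the latest possible date, and stops in the same month or year get the last-dose date. Likewise, a course begun on the 20th and stopped in that same month receives a stop on the 1st only in months after the last-dose month; in earlier months it receives the month end.

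A reader might also infer that the medication tables are distorted throughout. The documents do not support that either. Table 1 looks at the window each date falls in, not at date order, so many inverted records keep a proper label: on the day-missing grid, 193,305 − 47,117 = 146,188 inverted records are not *Data error*. A medicine started by last dose + 28 stays in *During* under these branches. SAP Table 2 selects concomitant CNS depressants during dosing by start date, so it does not turn on the stop. The *Data error* cell at least makes the worst records visible, and the protocol's follow-up contact asks for outstanding stop dates and its data-management sections provide for queries, which should reduce partial dates.

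Finally, latest-date completion does not remove misclassification; it reverses its direction. That stands, and it makes the choice of direction partly a preference. What survives all of this is the missing start-date floor and the one-way loss of *Post* labels.

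The stop-date branches mirror the start-date branches, which may suggest that one was copied from the other. The documents do not say so, and nothing here depends on it.

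**Conclusion.** The point holds for partial stop dates in or after the last-dose month or year. As written, the rule can place a stop before its start, can turn a valid post-dosing record into *Data error*, and can label post-dosing use *During* only. The error in the period label runs towards understating post-dosing use.

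The figure of 336 of 365 is plain calendar arithmetic. The 52% and 96% rest on the even-grid assumptions above and on the stop being partial. The documents give no count of partial stop dates, so the number of affected records cannot be stated. The outputs are descriptive medication summaries in a single-group open-label study, and no inferential result depends on them. Severity: minor.

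**What to change.** Two changes to SAP 20.8.

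1. State that a completed stop date is never earlier than the known or completed start date. This is needed whichever direction is preferred. It alone empties the *Data error* cell of records created by imputation, because a start after last dose + 28 then forces the stop outside the window too.
2. For partial stops in or after the last-dose month or year, use the latest date consistent with the recorded part (month end or 31 December), capped at last contact. This agrees with Table 1's handling of a wholly missing stop when the start is missing or no later than last dose + 28. The branch for earlier months and years can stay.

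On the same grids, with last contact at last dose + 56, both changes together reduce the lost *Post* labels from 5,348 and 9,814 to 0, and inversions and imputed *Data error* records to 0.

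The cost is a few lines of SAP text, one derivation, and over-counting in the other direction. Of the 10,585 grid combinations with a true stop by last dose + 28, 5,366 (51%, day missing) or 10,150 (96%, day and month missing) become *During, Post*, against none under the current rule. The SAP should say that this direction was chosen deliberately.

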20.9 CHARACTER VALUES OF CLINICAL LABORATORY PARAMETERS AND OTHER LABORATORY IMPUTATION RULES

- If a reported value of a clinical laboratory parameter cannot be used in a statistical summary table due, for example, to the fact that a character string is reported for a parameter of the numerical type, a coded value needs to be appropriately determined and used in the statistical analyses. Value of X+0.0001 will be used to impute ">X" character value and X-0.0001 will be used to impute "<X". That is, if X equal to 60, 60.0001 will be used to impute character value of ">60" and 59.999 will be used to impute "<60". However, the actual values as reported in the database may be presented in data listings.
- Due to the fact that screening lab records were rolled-over from RB-US-13-0003, whose LDH, total bilirubin and AST records have lower limits and HDL-C records have upper limit as opposed to at visits after first injection only having one-sided upper limits for parameters LDH, total bilirubin and AST and one-sided lower limit for HDL-C, lab classification values (i.e., Low, normal and high) for parameters LDH, total bilirubin and AST and HDL-C at screening and from RB-US-13-0003 should be imputed so that shift tables can be tabulated. The imputation rules are as follows:
 - For screening records (ie, rolled-over from RB-US-13-0003) of parameters LDH, total bilirubin and AST, lower limits will be imputed as 0. The lab character values of "Low" and "Normal" will be collapsed to be "Normal".
 - For screening records (ie, rolled-over from RB-US-13-0003) of HDL-C, upper limit will be imputed as blank. The lab character values of "Normal" and "High" will be collapsed to be "Normal".
- GGT assessments at Screening have categories of normal and high but have three categories of low, normal and high post-baseline. Then for GGT post-baseline assessments, low and normal will be collapsed to normal.

20.10 C-SSRS DATA IMPUTATION

In the Suicidal Behavior section, when the answer to the question "Have you made a suicide attemp" is NO, then the "Total # of Attempts" should be 0. In our clincial database, we have both 0 and Blank present. In the analysis dataset, under this scenario, Blank for Total # of Attempts will be imputed as 0.

No changes have been made to analyses specified in protocol.

22.0 **REFERENCES**

Guidance for Industry Drug-Induced Liver Injury: Premarketing Clinical Evaluation:
U.S. Department of Health and Human Services Food and Drug Administration Center
for Drug Evaluation and Research (CDER) Center for Biologics Evaluation and
Research (CBER)

23.0

APPENDIX

23.1 APPENDIX 1: LIST OF PREFERRED TERMS FROM STANDARD MEDDRA QUERIES FOR ADVERSE EVENTS OF SPECIAL INTEREST

LIST OF PREFERRED TERMS FOR PSYCHIATRIC HISTORY

Adjustment disorder with anxiety	Cyclothymic disorder
Adjustment disorder with depressed mood	Bipolar disorder
Adjustment disorder with disturbance of conduct	Hypomania
Adjustment disorder with mixed anxiety and depressed mood	Mania
Adjustment disorder with mixed disturbance of emotion and conduct	Blunted affect
Grief reaction	Constricted affect
Adjustment disorder	Flat affect
Agitation	Inappropriate affect
Agitation neonatal	Affect lability
Anticipatory anxiety	Affective ambivalence
Anxiety	Anger
Nervousness	Dysphoria
Stress	Emotional disorder
Tension	Emotional poverty
Activation syndrome	Euphoric mood
Acute stress disorder	Irritability
Post-traumatic stress disorder	Moaning
Postpartum stress disorder	Mood altered
Burnout syndrome	Emotional distress
Anniversary reaction	Neuroleptic-induced deficit syndrome
Acrophobia	Alexithymia
Agoraphobia	Frustration tolerance decreased
Animal phobia	Mood swings
Claustrophobia	Affective disorder
Fear	Apathy
Fear of animals	Listless
Fear of closed spaces	Mood disorder due to a general medical condition
Fear of disease	Seasonal affective disorder
Fear of open spaces	Boredom

Fear of weight gain	Laziness
Performance fear	Substance-induced mood disorder
Phobia	Aggression
Phobia of exams	Antisocial behaviour
Phobia of flying	Asocial behaviour
Phobic avoidance	Attention-seeking behaviour
Social anxiety disorder	Belligerence
Social fear	Disinhibition
Fear of falling	Grandiosity
Dysmorphophobia	Hostility
Ochlophobia	Indifference
Phagophobia	Inferiority complex
Fear of crowded places	Negativism
Fear of eating	Paranoia
Arachnophobia	Personality change
Hydrophobia	Social avoidant behaviour
Phonophobia	Soliloquy
Phobia of driving	Suspiciousness
Noctiphobia	Violence-related symptom
Nocturnal fear	Homicidal ideation
Osmophobia	Impatience
Nosophobia	Disturbance in social behaviour
Photoaugiaphobia	Aversion
Thanatophobia	Suggestibility
Fear of death	Stubbornness
Fear of pregnancy	Pseudologia
Haphephobia	Overconfidence
Paruresis	Egocentrism
Pharmacophobia	Defiant behaviour
Emetophobia	Personality disorder
Autophobia	Pithiatism
Haemophobia	Self esteem decreased
Fear of injection	Self esteem inflated
Thermophobia	Avoidant personality disorder
Algophobia	Dependent personality disorder
Limited symptom panic attack	Obsessive-compulsive personality disorder
Panic attack	Antisocial personality disorder
Panic disorder	Borderline personality disorder
Panic reaction	Histrionic personality disorder

Compulsions	Narcissistic personality disorder
Obsessive thoughts	Psychopathic personality
Obsessive-compulsive disorder	Paranoid personality disorder
Trichotillomania	Schizoid personality disorder
Body dysmorphic disorder	Schizotypal personality disorder
Obsessive rumination	Breath holding
Dermatillomania	Staring
Compulsive lip biting	Regressive behaviour
Nail picking	Abnormal behaviour
Compulsive shopping	Sexually inappropriate behaviour
Compulsive hoarding	Behaviour disorder due to a general medical condition
Compulsive handwashing	Scatolia
Paediatric autoimmune neuropsychiatric disorders associated with streptococcal infection	Neglect of personal appearance
Trichotemnomania	Trance
Compulsive cheek biting	Hypervigilance
Obsessive need for symmetry	Abulia
Obsessive-compulsive symptom	Psychiatric symptom
Anxiety disorder due to a general medical condition	Psychiatric decompensation
Generalised anxiety disorder	Decreased eye contact
Neurosis	Psychological trauma
Postpartum neurosis	Helplessness
Selective mutism	Personality change due to a general medical condition
Separation anxiety disorder	Mental disorder due to a general medical condition
Anxiety disorder	Neuropsychiatric syndrome
Catatonia	Psychological factor affecting medical condition
Restlessness	Mental status changes
Automatism	Dyslogia
Automatism epileptic	Mental disorder
Automatism, command	Emotional disorder of childhood
Bruxism	Neurotic disorder of childhood
Echolalia	Personality disorder of childhood
Echopraxia	Reactive attachment disorder of infancy or early childhood
Head banging	School refusal
Posturing	Disinhibited social engagement disorder of childhood
Stereotypy	Encopresis
Waxy flexibility	Enuresis

Tic	Alcohol abuse
Chronic tic disorder	Alcohol problem
Complex tic	Alcoholic hangover
Provisional tic disorder	Alcoholism
Secondary tic	Dependence
Attention deficit/hyperactivity disorder	Drug abuse
Atypical attention deficit syndrome	Drug dependence
Oppositional defiant disorder	Drug dependence, antepartum
Conduct disorder	Drug dependence, postpartum
Disruptive mood dysregulation disorder	Tobacco abuse
Change in sustained attention	Withdrawal syndrome
Distractibility	Alcohol withdrawal syndrome
Daydreaming	Nicotine dependence
Executive dysfunction	Tobacco withdrawal symptoms
Vascular cognitive impairment	Neonatal complications of substance abuse
Mental fatigue	Substance abuse
Learning disability	Dopamine dysregulation syndrome
Reading disorder	Binge drinking
Learning disorder	Substance dependence
Mutism	Gambling disorder
Communication disorder	Brief psychotic disorder, with postpartum onset
Speech sound disorder	Brief psychotic disorder with marked stressors
Clang associations	Transient psychosis
Logorrhea	Brief psychotic disorder without marked stressors
Neologism	Alice in wonderland syndrome
Verbigeration	Delusional disorder, erotomaniac type
Taciturnity	Delusional disorder, grandiose type
Disorganized speech	Delusional disorder, jealous type
Coprolalia	Delusional disorder, mixed type
Lack of spontaneous speech	Delusional disorder, somatic type
Poverty of speech	Delusional disorder, unspecified type
Pressure of speech	Delusional disorder, persecutory type
Screaming	Acute psychosis
Dysphemia	Alcoholic psychosis
Confusional state	Psychotic behaviour
Disorientation	Senile psychosis
Delirium	Shared psychotic disorder
Delirium tremens	Reactive psychosis
Delirium febrile	Epileptic psychosis

Post-traumatic amnestic disorder	Childhood psychosis
Korsakoff's syndrome	Psychotic disorder
Paramnesia	Psychotic disorder due to a general medical condition
Pseudodementia	Hysterical psychosis
Behavioural and psychiatric symptoms of dementia	Postictal psychosis
Agitated depression	Substance-induced psychotic disorder
Depression	Rebound psychosis
Depression suicidal	Parkinson's disease psychosis
Postpartum depression	Schizoaffective disorder
Major depression	Schizophreniform disorder
Menopausal depression	Schizoaffective disorder bipolar type
Childhood depression	Schizoaffective disorder depressive type
Post stroke depression	Schizophrenia
Postictal depression	Anorgasmia
Persistent depressive disorder	Female orgasmic disorder
Anhedonia	Male orgasmic disorder
Decreased interest	Orgasm abnormal
Depressed mood	Premature ejaculation
Feeling of despair	Orgasmic sensation decreased
Feelings of worthlessness	Psychosexual disorder
Morose	Sex dysphoria
Psychomotor retardation	Sexual inhibition
Tearfulness	Psychogenic erectile dysfunction
Feeling guilty	Disturbance in sexual arousal
Depressive symptom	Excessive masturbation
Negative thoughts	Libido decreased
Sense of a foreshortened future	Libido increased
Autism spectrum disorder	Loss of libido
Neurodevelopmental disorder	Sexual aversion disorder
Dissociation	Excessive sexual fantasies
Dissociative amnesia	Libido disorder
Dissociative disorder	Hypersexuality
Dissociative identity disorder	Compulsive sexual behaviour
Depersonalisation/derealisation disorder	Genito-pelvic pain/penetration disorder
Delusion	Exhibitionism
Delusion of grandeur	Fetishism
Delusion of reference	Frotteurism
Delusion of replacement	Masochism

Erotomanic delusion	Paedophilia
Jealous delusion	Paraphilia
Persecutory delusion	Sadism
Somatic delusion	Transvestism
Thought insertion	Voyeurism
Thought withdrawal	Initial insomnia
Thought broadcasting	Insomnia
Cotard's syndrome	Middle insomnia
Depressive delusion	Hyposomnia
Mixed delusion	Terminal insomnia
Deja vu	Behavioural insomnia of childhood
Delusional perception	Breathing-related sleep disorder
Derealisation	Dyssomnia
Flashback	Hypnagogic hallucination
Hallucination	Hypnopompic hallucination
Hallucination, auditory	Sleep attacks
Hallucination, gustatory	Abnormal dreams
Hallucination, olfactory	Nightmare
Hallucination, tactile	Rapid eye movements sleep abnormal
Hallucination, visual	Sleep talking
Hallucinations, mixed	Sleep terror
Illusion	Somnambulism
Jamais vu	Abnormal sleep-related event
Somatic hallucination	Parasomnia
Hallucination, synaesthetic	Loss of dreaming
Paroxysmal perceptual alteration	Sleep-related eating disorder
Time perception altered	Sleep sex
Autoscopy	Sleep inertia
Circumstantiality	Confusional arousal
Confabulation	Rapid eye movement sleep behaviour disorder
Derailment	Sleep disorder due to general medical condition, hypersomnia type
Flight of ideas	Sleep disorder due to general medical condition, insomnia type
Ideas of reference	Sleep disorder due to general medical condition, mixed type
Illogical thinking	Sleep disorder due to general medical condition, parasomnia type
Loose associations	Sleep disorder due to a general medical condition
Magical thinking	Sleep disorder

Perseveration	Hypersomnia-bulimia syndrome
Poverty of thought content	Sopor
Tangentiality	Hypersomnia related to another mental condition
Thinking abnormal	Insomnia related to another mental condition
Thought blocking	Completed suicide
Bradyphrenia	Intentional self-injury
Morbid thoughts	Suicidal ideation
Intellectualisation	Suicide attempt
Tachyphrenia	Self-injurious ideation
Impaired reasoning	Self injurious behaviour
Paralogism	Suicidal behaviour
Pathological doubt	Suicide threat
Intrusive thoughts	Compensation neurosis
Purging	Munchausen's syndrome
Self-induced vomiting	Factitious disorder
Eating disorder symptom	Conversion disorder
Anorexia and bulimia syndrome	Polydipsia psychogenic
Anorexia nervosa	Psychogenic dysuria
Binge eating	Torticollis psychogenic
Bulimia nervosa	Vomiting psychogenic
Eating disorder	Psychosomatic disease
Merycism	Pseudoneurologic symptom
Pica	Psychogenic seizure
Food aversion	Psychogenic movement disorder
Selective eating disorder	Psychogenic tremor
Impulsive behaviour	Psychogenic respiratory distress
Intermittent explosive disorder	Somatoform genitourinary disorder
Kleptomania	Somatic symptom disorder
Poriomania	Illness anxiety disorder
Pyromania	Cardiovascular somatic symptom disorder
Onychophagia	Gastrointestinal somatic symptom disorder
Impulse-control disorder	Neurologic somatic symptom disorder
Necromania	Cutaneous somatic symptom disorder
Clinomania	Somatic symptom disorder of pregnancy
Bipolar I disorder	
Bipolar II disorder	

**CUSTOMIZED MEDDRA QUERY (CMQ) LIST OF PREFERRED TERMS FOR
DRUG RELATED HEPATIC DISORDERS**

Cholestasis and jaundice of hepatic origin	
Bilirubin excretion disorder	Jaundice
Cholaemia	Jaundice cholestatic
Cholestasis	Jaundice hepatocellular
Cholestatic liver injury	Mixed liver injury
Cholestatic pruritus	Ocular icterus
Drug-induced liver injury	Parenteral nutrition associated liver disease
Hepatitis cholestatic	Deficiency of bile secretion
Hyperbilirubinaemia	Yellow skin
Icterus index increased	
Hepatic failure, fibrosis and cirrhosis and other liver damage-related conditions	
Acute hepatic failure	Liver and small intestine transplant
Acute on chronic liver failure	Liver dialysis
Acute yellow liver atrophy	Liver disorder
Ascites	Liver injury
Asterixis	Liver operation
Bacterascites	Liver transplant
Biliary cirrhosis	Lupoid hepatic cirrhosis
Biliary cirrhosis primary	Minimal hepatic encephalopathy
Biliary fibrosis	Mixed liver injury
Cholestatic liver injury	Nodular regenerative hyperplasia
Chronic hepatic failure	Non-alcoholic fatty liver
Coma hepatic	Non-alcoholic steatohepatitis
Cryptogenic cirrhosis	Non-cirrhotic portal hypertension
Diabetic hepatopathy	Oedema due to hepatic disease
Drug-induced liver injury	Oesophageal varices haemorrhage
Duodenal varices	Peripancreatic varices
Gallbladder varices	Portal fibrosis
Gastric variceal injection	Portal hypertension
Gastric variceal ligation	Portal hypertensive enteropathy
Gastric varices	Portal hypertensive gastropathy
Gastric varices haemorrhage	Portal vein cavernous transformation

Hepatectomy	Portal vein dilatation
Hepatic atrophy	Porto pulmonary hypertension
Hepatic calcification	Renal and liver transplant
Hepatic cirrhosis	Retrograde portal vein flow
Hepatic encephalopathy	Reye's syndrome
Hepatic encephalopathy prophylaxis	Reynold's syndrome
Hepatic failure	Splenic varices
Hepatic fibrosis	Splenic varices haemorrhage
Hepatic hydrothorax	Steatohepatitis
Hepatic infiltration eosinophilic	Subacute hepatic failure
Hepatic lesion	Varices oesophageal
Hepatic necrosis	Varicose veins of abdominal wall
Hepatic steato-fibrosis	Anorectal varices
Hepatic steatosis	Anorectal varices haemorrhage
Hepatitis fulminant	Intrahepatic portal hepatic venous fistula
Hepatobiliary disease	Peritoneovenous shunt
Hepatocellular foamy cell syndrome	Portal shunt
Hepatocellular injury	Portal shunt procedure
Hepatopulmonary syndrome	Small-for-size liver syndrome
Hepatorenal failure	Spider naevus
Hepatorenal syndrome	Splenorenal shunt
Hepatotoxicity	Splenorenal shunt procedure
Intestinal varices	Spontaneous intrahepatic portosystemic venous shunt
Intestinal varices haemorrhage	Stomal varices
Varicose vein	
Hepatitis, non-infectious	
Acute graft versus host disease in liver	Hepatitis fulminant
Allergic hepatitis	Hepatitis toxic
Autoimmune hepatitis	Ischaemic hepatitis
Chronic graft versus host disease in liver	Lupus hepatitis
Chronic hepatitis	Non-alcoholic steatohepatitis
Graft versus host disease in liver	Radiation hepatitis
Hepatitis	Steatohepatitis
Hepatitis acute	Granulomatous liver disease
Hepatitis cholestatic	Liver sarcoidosis
Hepatitis chronic active	Portal tract inflammation

Hepatitis chronic persistent	
Liver related investigations, signs and symptoms	
Alanine aminotransferase abnormal	Hypercholia
Alanine aminotransferase increased	Hypertransaminasaemia
Ammonia abnormal	Kayser-Fleischer ring
Ammonia increased	Liver function test abnormal
Ascites	Liver induration
Aspartate aminotransferase abnormal	Liver palpable
Aspartate aminotransferase increased	Liver scan abnormal
Bacterascites	Liver tenderness
Bile output abnormal	Mitochondrial aspartate aminotransferase increased
Bile output decreased	Molar ratio of total branched-chain amino acid to tyrosine
Biliary ascites	Oedema due to hepatic disease
Bilirubin conjugated abnormal	Perihepatic discomfort
Bilirubin conjugated increased	Retrograde portal vein flow
Bilirubin urine present	Total bile acids increased
Biopsy liver abnormal	Transaminases abnormal
Blood bilirubin abnormal	Transaminases increased
Blood bilirubin increased	Ultrasound liver abnormal
Blood bilirubin unconjugated increased	Urine bilirubin increased
Bromosulphthalein test abnormal	X-ray hepatobiliary abnormal
Child-Pugh-Turcotte score abnormal	5'nucleotidase increased
Child-Pugh-Turcotte score increased	Blood alkaline phosphatase abnormal
Computerised tomogram liver	Blood alkaline phosphatase increased
Foetor hepaticus	Blood cholinesterase abnormal
Galactose elimination capacity test abnormal	Blood cholinesterase decreased
Galactose elimination capacity test decreased	Deficiency of bile secretion
Gamma-glutamyltransferase abnormal	Glutamate dehydrogenase increased
Gamma-glutamyltransferase increased	Haemorrhagic ascites
Guanase increased	Hepatic fibrosis marker abnormal
Hepaplastin abnormal	Hepatic fibrosis marker increased
Hepaplastin decreased	Hypoalbuminaemia
Hepatic artery flow decreased	Leucine aminopeptidase increased
Hepatic congestion	Liver function test decreased
Hepatic enzyme abnormal	Liver function test increased

Hepatic enzyme decreased	Liver iron concentration abnormal
Hepatic enzyme increased	Liver iron concentration increased
Hepatic function abnormal	Model for end stage liver disease score abnormal
Hepatic hydrothorax	Model for end stage liver disease score increased
Hepatic hypertrophy	Periportal oedema
Hepatic mass	Peritoneal fluid protein abnormal
Hepatic pain	Peritoneal fluid protein decreased
Hepatic sequestration	Peritoneal fluid protein increased
Hepatic vascular resistance increased	Pneumobilia
Hepatobiliary scan abnormal	Portal vein flow decreased
Hepatomegaly	Portal vein pressure increased
Hepatosplenomegaly	Retinol binding protein decreased
Hyperammonaemia	Urobilinogen urine decreased
Hyperbilirubinaemia	Urobilinogen urine increased
Hepatic disorders specifically reported as alcohol-related	
Alcoholic liver disease	Hepatic steato-fibrosis
Cirrhosis alcoholic	Hepatitis alcoholic
Fatty liver alcoholic	Zieve syndrome

CMQ LIST OF PREFERRED TERMS FOR INJECTION SITE REACTION

Immediate post-injection reaction	Injection site ulcer
Injection related reaction	Injection site urticaria
Injection site abscess	Injection site vesicles
Injection site cellulitis	Injection site warmth
Injection site infection	Injection site ischaemia
Injection site pustule	Injection site coldness
Injection site abscess sterile	Injection site discolouration
Injection site anaesthesia	Injection site photosensitivity reaction
Injection site atrophy	Injection site swelling
Injection site bruising	Injection site discomfort
Injection site cyst	Injection site calcification
Injection site dermatitis	Injection site movement impairment
Injection site erosion	Injection site lymphadenopathy
Injection site erythema	Injection site nodule
Injection site extravasation	Embolia cutis medicamentosa

Injection site fibrosis	Injection site scar
Injection site granuloma	Injection site discharge
Injection site haematoma	Injection site pallor
Injection site haemorrhage	Injection site papule
Injection site hypersensitivity	Injection site injury
Injection site hypertrophy	Injection site scab
Injection site induration	Injection site eczema
Injection site inflammation	Injection site streaking
Injection site irritation	Injection site dryness
Injection site mass	Injection site laceration
Injection site necrosis	Injection site macule
Injection site nerve damage	Injection site vasculitis
Injection site oedema	Injection site exfoliation
Injection site pain	Injection site dysaesthesia
Injection site paraesthesia	Injection site plaque
Injection site phlebitis	Injection site hyperaesthesia
Injection site pruritus	Injection site hypoesthesia
Injection site rash	Injection site hypertrichosis
Injection site reaction	
Injection site thrombosis	

CMQ LIST OF PREFERRED TERMS FOR CNS DEPRESSION

Mental fatigue	Hyporesponsive to stimuli
Microsleep	Benign familial neonatal convulsions
Narcolepsy	Febrile convulsion
Coma	Drug withdrawal convulsions
Impaired driving ability	Convulsion neonatal
Impaired ability to use machinery	Convulsions local
Accident	Tonic convulsion
Road traffic accident	Convulsion in childhood
Vision blurred	Clonic convulsion
Vertigo CNS origin	Acute encephalitis with refractory, repetitive partial seizures
Incoherent	Generalised tonic-clonic seizure
Disturbance in attention	Complex partial seizures

Judgement impaired	Psychomotor seizures
Mental impairment	Simple partial seizures
Borderline mental impairment	Autonomic seizure
Cognitive disorder	Atonic seizures
Altered state of consciousness	Seizure
Depressed level of consciousness	Partial seizures with secondary generalisation
Lethargy	Alcoholic seizure
Loss of consciousness	Partial seizures
Sedation	Seizure like phenomena
Somnolence	Seizure cluster
Somnolence neonatal	Change in seizure presentation
Stupor	Migraine-triggered seizure
Syncope	Psychogenic seizure
Postictal state	Seizure anoxic
Consciousness fluctuating	Post stroke seizure
Neonatal oversedation	Accidental death
Hypoglycaemic unconsciousness	Accidental overdose
Hyperglycaemic unconsciousness	Accidental exposure to product
Post-injection delirium sedation syndrome	Cerebrovascular accident
Preictal state	Dizziness
Psychogenic pseudosyncope	Dizziness exertional
Mental status changes	Dizziness postural
Mental status changes postoperative	Procedural dizziness
Slow response to stimuli	Neurotoxicity
Unresponsive to stimuli	

CMQ LIST OF PREFERRED TERMS FOR RESPIRATORY DEPRESSION/RESPIRATORY FAILURE

Acute respiratory distress syndrome	Neonatal respiratory arrest
Acute respiratory failure	Neonatal respiratory depression
Apnoea	Neonatal respiratory distress syndrome
Apnoea neonatal	Neonatal respiratory failure
Infantile apnoea	Respiratory arrest
Apnoeic attack	Respiratory depression
Bradypnoea	Respiratory depth decreased

Breath sounds absent	Respiratory distress
Cardio-respiratory distress	Respiratory failure
Central-alveolar hypoventilation	Respiratory paralysis
Chronic respiratory failure	Respiratory rate decreased
Hypopnoea	Severe acute respiratory syndrome
Hypoventilation	Cardio-respiratory arrest
Hypoventilation neonatal	Cardio-respiratory arrest neonatal
Lung hypoinflation	Cardiopulmonary failure
Meconium aspiration syndrome	

CMQ LIST OF PREFERRED TERMS FOR ORTHOSTATIC HYPOTENSION

Orthostatic hypotension	Syncope
Vision blurred	Presyncope
Dizziness	Diastolic hypotension
Dizziness exertional	Hypotension
Dizziness postural	

CMQ LIST OF PREFERRED TERMS FOR WITHDRAWAL SYMPTOMS

Agitation	Malaise
Anxiety	Muscle spasms
Arthralgia	Muscle twitching
Bone pain	Myalgia
Chills	Mydriasis
Decreased appetite	Nausea
Depression	Piloerection
Diarrhoea	Pruritus
Dizziness	Psychomotor hyperactivity
Drug dependence	Pyrexia
Flushing	Respiratory rate increased
Heart rate increased	Restlessness
Hyperhidrosis	Rhinitis
Hypertension	Rhinorrhoea
Hypervigilance	Sneezing
Influenza like illness	Tachycardia

Insomnia	Tremor
Irritability	Vomiting
Lacrimal disorder	Yawning
Lacrimation increased	Drug withdrawal symptoms
Muscle strain	

CMQ LIST OF PREFERRED TERMS FOR ACUTE PANCREATITIS

Amylase abnormal	Oedematous pancreatitis
Amylase creatinine clearance ratio abnormal	Pancreatic abscess
Amylase increased	Pancreatic enzyme abnormality
Bilirubin conjugated abnormal	Pancreatic enzymes abnormal
Blood bilirubin increased	Pancreatic enzymes increased
Blood trypsin increased	Pancreatic haemorrhage
Cullen's sign	Pancreatic necrosis
Grey Turner's sign	Pancreatic phlegmon
Haemorrhagic necrotic pancreatitis	Pancreatic pseudocyst
Hereditary pancreatitis	Pancreatic pseudocyst drainage
Hyperamylasaemia	Pancreatitis
Hyperbilirubinaemia	Pancreatitis acute
Hyperlipasaemia	Pancreatitis haemorrhagic
Ischaemic pancreatitis	Pancreatitis necrotising
Lipase abnormal	Pancreatitis relapsing
Lipase increased	Pancreatorenal syndrome
Lipase urine increased	

